11.1 Patient Disposition

Study completion and discontinuation details, eligibility, treatment schedule allocation, population assignment, and protocol deviations will be listed.

The number of patients screened and treated, and the primary reason for study treatment discontinuation will be tabulated by treatment sequence.

The number and percentage of patients in each analysis population will be tabulated by treatment sequence.

The number and percentage of patients with major protocol deviations by treatment sequence will be tabulated.

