7.1 Sample Size

Up to 20 patients, both male and female, aged 0 – < 21 years of age will be recruited.

There are no power calculations in this trial. The objective of this trial is to estimate the population pharmacokinetics of 13-CRA following the administration of 13-CRA liquid (test product) and extracted capsule (reference product). From a statistical point of view, the collected plasma 13-CRA concentration data are expected to relate to a non-linear, mixed effects model involving repeated measures. The developed pharmacokinetic model will estimate the parameters of the model and their associated within- and between-patient variability.

In order to develop a robust population pharmacokinetic model (i.e. precisely estimated parameters), data from a minimum of 150 blood samples will be required. It is hoped that the required number of samples may be obtained from 12-18 patients. However, if problems are encountered in obtaining samples further patients may be included in the trial.

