7.2 Randomisation

Prior to the initiation of the trial 13-CRA, patients will be randomised to receive either liquid or extracted capsule formulation in “My –CRA month 1”. The patients will then cross-over to the alternative formulation in “My-CRA month 2”. After the trial if a patient requires additional cycles of 13-CRA, the patient will revert to standard 13-CRA therapy i.e. extracted capsules according to local practice.

Randomisation will be done centrally by Nova according to a randomisation list generated by the trial statistician, investigators will email (or telephone) Nova to receive randomisation details, this will be confirmed by email as “liquid first” or “extracted capsules first”, pharmacy contacts will also be notified.

8 Major Protocol Deviations

Protocol violations are any deviations from the procedures outlined in the protocol, for example, missed evaluations, incorrect timing of evaluations, non-compliance with investigation medical product (IMP) and intake of prohibited medications. It is the investigator’s responsibility to make all reasonable efforts to avoid protocol violations in order to avoid possible exclusion of the patient from the trial and/or analyses.

Major protocol deviations are defined as those deviations from the study protocol that may have the ability to impact the study results.

Major protocol deviations include (but are not limited to):

- Deviation from inclusion/exclusion criteria
- Withdrawal criteria met during the study but patient was not withdrawn
- Missed evaluations
- Incorrect timing of evaluations
- Prohibited concomitant medications
- Non-compliance with IMP

Where possible; major deviations will be programmatically generated. Listings of concomitant medications will be provided to the sponsor for review to identify prohibited medications prior to database freeze.

Major protocol deviations will result in exclusion from the pharmacokinetic population if they are considered likely to affect the determination of the pharmacokinetic parameters.

9 Analysis Populations

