11.4 Concomitant Medications

Concomitant medications recorded during the study will be coded using eMIMS. Details of concomitant medication will be listed.

Concomitant medications will be summarized according to whether they were being taken pre-study (prior medications) and/or during the study (concomitant). Prior medications are any that were being taken prior to the first dose of study medication (medication stop date prior to the first dose of study medication). Concomitant medications are any that were being taken on or after the first dose of study medication. If the start and stop dates of the concomitant medications do not clearly define the period during which a medication was taken, it will be assumed to be a concomitant medication.

Prior and concomitant medications will be summarized by treatment sequence, system class and sub-class.

12 Pharmacokinetic Assessments

The population PK analysis detailed in the protocol is not within the scope of this SAP.

Blood samples for measurement of 13-CRA and its metabolite 4-oxo-13-cis-RA will be obtained over the course of 6 hours after each dose. An additional sample 24-48 hours after day 14 will be obtained if possible.

Plasma concentrations will be expressed in ng/mL. All concentrations below the limit of quantification or missing data will be labelled as such in the concentration data listings. Concentrations below the limit of quantification will be treated as zero in summary statistics. Plasma concentrations will be listed and summarised by treatment group, day, and nominal time. In addition, individual plasma concentration-time plots, and mean plasma concentration-time plots by dose will be provided.

PK parameters will be listed. Additionally, PK parameters will be summarised by treatment group and day.

13 Safety

Safety will be assessed from records of adverse events (AEs), oro-pharyngeal tolerability, vital signs and results of physical examination.

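### The planned summary tables of treatment discontinuation and major deviations are split by randomised sequence only, so they do not show which product was stopped, mainly for stops not caused by adverse events

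*SAP*

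**What the plan says.** SAP 11.1 plans the disposition table as follows: "The number of patients screened and treated, and the primary reason for study treatment discontinuation will be tabulated by treatment sequence". For deviations it says: "The number and percentage of patients with major protocol deviations by treatment sequence will be tabulated". SAP 11.4 treats medications in the same way: "Prior and concomitant medications will be summarized by treatment sequence, system class and sub-class".

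The design is in SAP 7.2. Patients are randomised to liquid or extracted capsules for the first month, and then: "The patients will then cross-over to the alternative formulation in" the second month. Each sequence therefore contains one cycle of each product.

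The table list in SAP 17.1 has one table for each of these items (14.1.1, 14.1.2, and 14.1.6 with 14.1.7) and no further version by product or month. The total group introduced in SAP 16 replaces the age split; it does not add a product split.

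Other outputs are by treatment: exposure (SAP 13.1), adverse events including those leading to discontinuation (SAP 13.2), oro-pharyngeal symptoms (SAP 13.2) and palatability (SAP 14). Discontinuation details and deviations are also listed per patient (SAP 11.1), with listings sorted by sequence, patient and treatment (SAP 17.3).

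**The concern.** Sequence is the right grouping for baseline characteristics, which precede both products. A stop or a within-cycle deviation happens while the patient is on one particular product. Counting by sequence adds first-month stops on liquid to second-month stops on capsules in one column, and the reverse in the other. If families give up mostly on one formulation, the two columns are expected to look alike.

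This bears on the secondary objectives of tolerability, palatability and acceptability (SAP 4.2). The discontinuation reasons in Protocol 8.1 include withdrawal of consent, protocol deviation and other, besides adverse events. A family that stops because of taste or difficulty giving the dose would probably fall under one of those. The palatability survey is done on Day 14 of each cycle (Protocol 4.8) and missing responses are not imputed (SAP 10.2), so a family that stops before Day 14 may also be absent from the palatability table. Among major deviations, non-compliance with the study product (SAP 8) is the kind that could differ between a patient's two cycles.

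**Working it through.** The documents give no discontinuation rate and no allocation ratio, so there is no planned figure to reproduce. The check is algebraic, followed by illustrations.

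**Inputs from the documents.** There are two sequences and two periods (SAP 7.2). The maximum is "Up to 20 patients, both male and female", and for the expected number: "It is hoped that the required number of samples may be obtained from 12-18 patients" (SAP 7.1). On power: "There are no power calculations in this trial" (SAP 7.1).

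**Assumptions.** Allocation is 1:1. Let p be the chance of stopping while on liquid and q the chance while on extracted capsules, the same in either month (no period effect). A patient who stops in the first month does not start the second product.

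**By sequence.**
- Liquid first: p + (1 − p)q = p + q − pq
- Capsules first: q + (1 − q)p = p + q − pq

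The two are identical for every p and q, so the expected difference between sequences is zero even when p and q are far apart.

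**By product, with n patients per sequence.**
- Started liquid: n + n(1 − q); expected stops are p times that number.
- Started capsules: n + n(1 − p); expected stops are q times that number.

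For n = 10, p = 0.30, q = 0:
- By sequence: 10 × 0.30 = 3 of 10 in each.
- Started liquid: 10 + 10 = 20; stops 0.30 × 20 = 6.
- Started capsules: 10 + 10 × 0.70 = 17; stops 0.

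Expected counts for a range of assumed rates:

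| Patients (per sequence) | p | q | Each sequence | Liquid | Capsules |
|---|---|---|---|---|---|
| 12 (6) | 0.40 | 0 | 2.4/6 | 4.8/12 | 0/9.6 |
| 18 (9) | 0.30 | 0 | 2.7/9 | 5.4/18 | 0/15.3 |
| 20 (10) | 0.30 | 0 | 3/10 | 6/20 | 0/17 |
| 20 (10) | 0.30 | 0.10 | 3.7/10 | 5.7/19 | 1.7/17 |
| 20 (10) | 0.50 | 0.10 | 5.5/10 | 9.5/19 | 1.5/15 |

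**Chance variation.** Exact binomial sums were run for 12, 18 and 20 patients with (p, q) = (0.30, 0), (0.40, 0), (0.30, 0.10) and (0.50, 0.10). The two sequences differ by at most one patient with probability 0.50 to 0.66. Under these assumptions a larger gap is chance. With a period effect the sequences need not tie, but the table still has no column that separates product from month.

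**What other outputs recover.**
- Stops caused by adverse events: shown per treatment (SAP 13.2).
- Shorter time on a product: shown by treatment, without the reason (SAP 13.1).
- Taste, spitting or vomiting, willingness, ease of dosing and preference: shown by treatment for those surveyed on Day 14 (SAP 14, Protocol 4.8).
- Stops for other reasons, by product: in no summary table.

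**The case against.** The strongest reply is that nothing is lost. Discontinuations, deviations, drug administration and concomitant medications are all listed per patient, and with at most 20 patients a reader can assign each event to a cycle by hand. That stands. A reader might infer from the sequence columns that product-specific stopping cannot be recovered, or that only discontinuations due to adverse events are seen by product. The documents support neither: the listings hold the data, and exposure and palatability by treatment cover part of the same ground.

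Second, discontinuation is not a listed endpoint (SAP 5), and a disposition table properly accounts for patients as randomised. That also stands, and is why the sequence columns should stay. A reader might further infer that the bioavailability result is affected. No estimate is computed from these tables, and the population pharmacokinetic analysis is outside this SAP (SAP 2 and 12).

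Third, attribution is not always clean.
- Families need not give a reason (Protocol 8.1), so a product column may often show only withdrawn consent.
- Refusal of further blood sampling also leads to withdrawal (Protocol 3.1) and says little about the product.
- The break between cycles is 14 days plus up to 7 (Protocol 1.1.3), when no product is being taken.
- Eligibility deviations belong to no cycle.

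These points do not remove the gap, but they mean the fix needs stated rules. For concomitant medications the objection largely succeeds: drugs taken throughout would appear under both products, and the split adds little.

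**Conclusion.** The point holds as a limited gap in summary reporting. The discontinuation and deviation tables in SAP 11.1 do not show which product was involved. With no period effect, the expected stopping proportion is p + q − pq in both sequences. In the assumed 20-patient example, 6/20 against 0/17 by product appears as 3/10 against 3/10 by sequence.

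The part that no other summary covers is stopping for reasons other than adverse events, including stops before the Day 14 survey. The result for sequences is general under no period effect. The counts depend on assumed stopping rates and 1:1 allocation, neither of which the documents give. The change is worth making because it serves the stated secondary objectives cheaply; no conclusion of the trial depends on it.

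**What to change.** In SAP 11.1 and Table 14.1.1, keep the sequence columns and add discontinuations and primary reasons by product and by month. Use as denominator the patients who started that product. State three rules:

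- A stop during the break between cycles is attributed to the last product taken and shown on a separate line.
- Withdrawal for refusal of blood sampling is shown separately where that reason is recorded.
- Stops with no stated reason are shown as such, under the product concerned.

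In Table 14.1.2, add the same split for deviations that occur within a cycle, such as non-compliance with the study product, missed or mistimed evaluations and prohibited medication. Leave eligibility deviations by sequence only.

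For Table 14.1.7, a split by product cycle is optional; if made, count a drug that spans both cycles in each. Leave prior medications by sequence.

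The cost is SAP wording, extra columns in two tables (three if the option is taken) and the attribution rules. The CRF already takes the discontinuation date and, where possible, the reason (Protocol 8.1), the product given (Protocol 3.5) and medication dates (Protocol 6.2). A deviation tied to a visit or dose takes the cycle of that visit or dose.

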11.2 Baseline and Demographic Characteristics

Demographic parameters will include age, gender, race, height (cm), weight (kg) and body mass index (BMI) (kg/m^2). Demographics will be listed and tabulated by treatment sequence using descriptive statistics.

11.3 Medical History

Details of non-oncology medical history will be listed including condition, start and stop dates, and whether any medication was taken. Partial dates may be recorded and no imputations will be made for missing or partial dates in the listing.

Oncology history data will also be listed, including start and stop dates, and whether any medication was taken. Partial dates may be recorded and no imputations will be made for missing or partial dates in the listing.

Medical histories will be coded according to the Medical Dictionary for Regulatory Activities (MedDRA) dictionary version in effect at the time of study activation. A summary of non-oncology and oncology medical histories and number of patients with a medical history will be presented by treatment sequence, system organ class and preferred term.

11.4 Concomitant Medications

Concomitant medications recorded during the study will be coded using eMIMS. Details of concomitant medication will be listed.

Concomitant medications will be summarized according to whether they were being taken pre-study (prior medications) and/or during the study (concomitant). Prior medications are any that were being taken prior to the first dose of study medication (medication stop date prior to the first dose of study medication). Concomitant medications are any that were being taken on or after the first dose of study medication. If the start and stop dates of the concomitant medications do not clearly define the period during which a medication was taken, it will be assumed to be a concomitant medication.

Prior and concomitant medications will be summarized by treatment sequence, system class and sub-class.

12 Pharmacokinetic Assessments

The population PK analysis detailed in the protocol is not within the scope of this SAP.

Blood samples for measurement of 13-CRA and its metabolite 4-oxo-13-cis-RA will be obtained over the course of 6 hours after each dose. An additional sample 24-48 hours after day 14 will be obtained if possible.

Plasma concentrations will be expressed in ng/mL. All concentrations below the limit of quantification or missing data will be labelled as such in the concentration data listings. Concentrations below the limit of quantification will be treated as zero in summary statistics. Plasma concentrations will be listed and summarised by treatment group, day, and nominal time. In addition, individual plasma concentration-time plots, and mean plasma concentration-time plots by dose will be provided.

PK parameters will be listed. Additionally, PK parameters will be summarised by treatment group and day.

13 Safety

Safety will be assessed from records of adverse events (AEs), oro-pharyngeal tolerability, vital signs and results of physical examination.

13.1 Treatment Exposure

Details of study drug administration will be listed.

The total dose received for each treatment, and time on treatment will be summarized by treatment, and listed.

Time on treatment for each treatment will be defined as last dose date for that treatment – first dose date for that treatment +1.

13.2 Adverse Events

AEs will be coded according to the latest version of the MedDRA dictionary. The severity of AEs will be coded according to the National Cancer Institute (NCI)-Common Terminology Criteria for Adverse Events (CTCAE) coding system version 4.03.

AEs will be deemed treatment emergent if they start on or after the time of the first dose of study medication.

All treatment emergent adverse events (TEAEs) and serious adverse events (SAEs) will be listed.

An overall adverse event summary will be presented for the categories: any TEAEs, any drug-related AEs, any Grade 3 or greater AEs, any Grade 3 or greater drug-related AEs, any TEAEs leading to death, any drug-related TEAEs leading to death, any serious TEAEs, any drug-related serious TEAEs, any TEAEs leading to discontinuations, and any drug-related TEAEs leading to discontinuations. Both number of events and number of patients will be tabulated. For patients, percentages will be calculated from the total number of patients per treatment.

Summaries of TEAEs and serious TEAEs will be tabulated by system organ class and preferred term sorted by decreasing frequency within system organ class (SOC). Both number of events and number of patients will be tabulated. For patients, percentages will be calculated from the total number of patients per treatment.

In addition, TEAEs and serious TEAEs will be summarized by maximum severity, system organ class and preferred term, and strongest relationship, system organ class and preferred term. If a patient experiences an adverse event more than once the event with the worst severity or at the most related to IMP occurrence will be considered. Patients will be included only once at each level where they experienced one or more events.

Oro-pharyngeal tolerability and symptoms will be separately assessed. Dry skin, peeling skin, cracked lips and dry eyes will be assessed by the investigator on a four point scale (0 = none, 1 = mild, 2 = moderate, and 3 = severe). Oro-pharyngeal symptoms will be assessed at baseline and following administration of 13-CRA during the Pharmacokinetic Day 14. Each symptom will be summarised by treatment and study day, presenting frequency counts and percentages for each value on the scale.

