## 5.2 Criteria Prior to starting each cycle of 13-CRA

1. Total bilirubin  $\leq 1.5$  x normal, and (SGPT) ALT  $\leq 5$  x normal. Veno-occlusive disease if present, should be stable or improving.
2. Skin toxicity no greater than CTCAE Grade 1
3. Serum triglycerides  $< 5.65$  mmol/L.
4. No haematuria and / or proteinuria on urinalysis.
5. Serum calcium  $\geq 2.0$  mmol/L to  $\leq 2.9$  mmol/L.
6. Serum creatinine based on age / gender as follows:

Age	Maximum Serum Creatinine $\mu$ mol/L	
	Male	Female
1 month to $< 6$ months	35	35
6 months to $< 1$ year	44	44
1 to $< 2$ years	53	53
2 to $< 6$ years	70	70
6 to $< 10$ years	88	88
10 to $< 13$ years	106	106
13 to $< 16$ years	132	124
$\geq 16$ years	150	124

7. Patients with a seizure disorder must be well controlled and taking anticonvulsants. CNS toxicity  $<$  grade 2 (CTCAE).

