# 6 TREATMENT OF PATIENTS

## 6.1 Evaluation of test and reference treatment

Evaluation of the test and reference product will occur during two months of the therapy only.

Consent to take part in the trial will be obtained before any trial procedures are undertaken.

Patients who are already receiving 13-CRA treatment will also be eligible for the trial, so long as they are able to commit to two cycles of trial 13-CRA. The next planned 14-day treatment cycle will be classed as My-CRA Month 1. After consent to take part has been obtained and prior to the initiation of the next 14 day treatment patients will be randomised to receive either 13-CRA liquid (test product) or liquid extracted from capsule (reference product) in My-CRA Month 1. Randomisation will be done once eligibility has been confirmed and their next scheduled treatment visit is booked, in order that the appropriate medication can be made available for the

patient's visit. Randomisation will be done centrally by Nova according to a randomisation list generated by the trial statistician, investigators will email (or telephone) Nova to receive randomisation details, this will be confirmed by email as "liquid first" or "extracted capsules first", pharmacy contacts will also be notified. After My-CRA month 1, patients will then cross over to the alternative formulation in My-CRA Month 2. In all other treatment cycles patients will revert to standard therapy i.e. liquid extracted from capsules. The pharmacokinetics of 13-CRA will be evaluated during test and reference treatments (My-CRA Month 1 and 2).

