### 9.1 Definition of adverse events

An AE is any untoward medical occurrence in a patient or clinical trial patient administered a pharmaceutical product and which does not necessarily have a causal relationship with this treatment. An AE can therefore be any unfavourable and unintended sign (including an abnormal laboratory finding), symptom, or disease temporally associated with the use of an IMP, whether or not related to the IMP.

During the trial, any worsening of conditions, signs or symptoms noted from the time of consenting to take part in the trial will be recorded as an AE.

All AEs that occur (whether treatment related or not) will be recorded in the CRF throughout the duration of the visit (and for 14 days post dosing if recorded on the diary card or spontaneously reported to hospital staff).

As far as possible, each AE must be described by its duration (start and end time and date or ongoing), its frequency (single episode, intermittent, continuous), its severity (mild, moderate, severe - see section 9.2), a causality assessment (coexisting disease, concomitant medication, the IMP, or other cause), its relationship to the IMP (unrelated, unlikely, possibly, probably, definitely – see Section 9.2), whether this influenced the course of the IMP, whether it required specific action or therapy, and outcome.

All medical conditions present at baseline should not be considered as AEs unless these have worsened during the trial phase. In cases of surgical or diagnostic procedures the condition/illness leading to such a procedure is considered as the AE rather than the procedure itself.

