### 11.2 Safety, tolerability and palatability analyses

Reporting of the safety data will be of a descriptive nature and presented using appropriate summary statistics (e.g. n, mean, SD, %CV, median, minimum, maximum) or frequency

distributions (n%) by age group (age 1-11 years, age 12-< 21 years). Unless otherwise stated these tabulations will be supported by data listings.

Safety summaries will include all patients irrespective of whether or not they completed the trial.

AEs will be coded according to the current version of MedDRA (version to be identified in trial report).

Treatment emergent adverse events (TEAEs) will be determined and only these will be included in the statistical analysis report. Details of the criteria of classifying an AE as a TEAE will be provided in the Statistical Analysis Plan.

The incidence of adverse events will be summarised by system organ class, preferred term and maximum severity. Adverse events will also be summarised by strongest relationship to Investigational Medicinal Product by event and system organ class. If a patient experiences an adverse event more than once the event with the worst severity or at the most related to IMP occurrence will be considered. Patients will be included only once at each level where they experienced one or more events.

A summary of the incidence of serious adverse events will be presented by event and system organ class.

Adverse events relating to oro-pharyngeal tolerability data will be additionally listed separately and appropriately summarised.

All results for other safety will be appropriately summarised.

Palatability data will be appropriately summarised.

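### SAP 13.2 defines treatment emergence by start date alone, so whether a worsened adverse event is tabulated, and under which product, depends on how its start is entered

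*SAP*

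**What the plan says.** Protocol 11.2 hands the definition to the SAP: "Details of the criteria of classifying an AE as a TEAE will be provided in the Statistical Analysis Plan". The same section makes that definition the filter for what is reported: "Treatment emergent adverse events (TEAEs) will be determined and only these will be included in the statistical analysis report".

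SAP 13.2 supplies one sentence: "AEs will be deemed treatment emergent if they start on or after the time of the first dose of study medication". It does not mention worsening, and it does not restart the test at the first dose of Month 2. Patient percentages in the AE tables use the number of patients per treatment as denominator, but no rule places an event under a treatment.

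Protocol 9.1 treats worsening as reportable: "any worsening of conditions, signs or symptoms noted from the time of consenting to take part in the trial will be recorded as an AE". It adds that "All medical conditions present at baseline should not be considered as AEs unless these have worsened during the trial phase". Each AE is described by a start, an end and a severity. Neither document says whether a recorded AE that worsens becomes a new record with a new start date.

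Two design features allow effects to be present already when a cycle starts. Protocol 6.1 states that "Patients who are already receiving 13-CRA treatment will also be eligible for the trial". The criteria for starting each cycle permit "Skin toxicity no greater than CTCAE Grade 1".

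**The concern.** Safety and tolerability are a secondary objective, and the SAP tabulates AEs by product. A drug effect that is already present at first dose, or at cross-over, and then becomes worse is information about the product being taken at that time. A rule based on start date alone has no place for it unless the site gives the worsening its own dated record. The result then rests on data-entry practice that neither document specifies.

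Two outcomes are at stake. Some worsened events could be missing from the TEAE tables by SOC and preferred term, by maximum severity and by relationship. Others could appear with their worst grade under the product the patient had already stopped.

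**Working it through.** The plan has no figure to reproduce, so the check sets the SAP rule against three cases and two ways of entering the data.

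| Case | One record, original start kept | Worsening dated at the change |
|---|---|---|
| A. Condition present at baseline, worsens after first dose | Start precedes first dose: not a TEAE | Start follows first dose: TEAE |
| B. AE arising between consent and first dose, worsens on product | Start precedes first dose: not a TEAE | New entry follows first dose: TEAE |
| C. AE starting in Month 1, worsens in Month 2 | TEAE; if attributed by start date, Month 1 product only | TEAE; the second entry can count against the Month 2 product |

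**Case A.** Under protocol 9.1 a baseline condition is not an AE until it worsens. The natural start of that AE is therefore the worsening, which puts the event in the right-hand column. It is lost only if a site enters the original onset.

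**Case B.** Protocol 9.1 runs from consent. Protocol 6.1 places consent and randomisation before the next scheduled cycle, so a window exists. Nothing says which column applies.

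**Case C.** The event is a TEAE with or without a worsening limb. What is missing is a rule that assigns it to a product.

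**Which events are exposed.** SAP 13.2 has the investigator score dryness and peeling of the skin, cracked lips and dry eyes from 0 to 3, at baseline and on Day 14. It summarises them by treatment and study day (Table 14.3.2.8), whatever their TEAE status. Hypercalcaemia, hepatotoxicity and triglycerides have no such table. SAP 5.2 has them noted as AEs if intervention is needed, and SAP 17.1 plans no laboratory table, so AE output is their only planned summary.

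**How the SAP treats other data.** SAP 13.4 takes a fresh vital-signs baseline at Day 1 of each treatment, and SAP 13.1 measures exposure from each treatment's own first dose. The TEAE rule has no such anchor.

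**Scale of one patient.** Inputs: up to 20 patients, with 12 to 18 hoped for (SAP 7.1). Assumption: every patient takes both products and so enters both denominators.
- One patient in one product's percentage: 1/20 = 5.0 points; 1/18 = 5.6; 1/12 = 8.3.
- Case C, mild on the Month 1 product and severe on the Month 2 product, held as one severe record attributed by start date: the severe row gains one patient under the Month 1 product and loses one under the Month 2 product. The difference between products moves by 2/20 = 10.0 points; 2/18 = 11.1; 2/12 = 16.7.

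The documents give no rates for events already present at first dose, persisting to Month 2 or worsening. The number of patients affected, and so the total effect, cannot be computed.

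**The case against.** A reader might infer that every event present at first dose that worsens is dropped. The documents do not support that. Case A is normally kept, for the reason given above, and the schedule in protocol Appendix I collects AEs from Day 1 and not at the pre-trial visit, which narrows case B. Three rows of the overall AE summary (drug-related events, events of Grade 3 or higher, and drug-related events of Grade 3 or higher) are not worded as TEAEs. SAEs are listed in any case.

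A reader might also infer that worsening dry skin or cracked lips disappears, or that the SAP charges a worsening to the wrong product. The scored table would show a symptom that is severe on Day 14 under the product being taken. No text allocates a spanning event at all, so misallocation is a possible result of silence and not a stated rule.

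Safety reporting is descriptive, with no test or decision rule. The SAP cites CRF version 2, which is not among the documents; its AE page may already say how a worsening is entered.

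These points limit the consequences but do not remove the gap. The scored table cannot show a worsening that comes and goes between scored visits, carries no relationship or seriousness, and covers four symptoms. The SOC, severity and relationship tables remain restricted to TEAEs. Whatever the CRF does, SAP 13.2 still lacks a worsening limb and an attribution rule.

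**Conclusion.** The concern holds in a limited form. SAP 13.2 rests on start date alone, anchored to a single first dose, and has no attribution rule. Exclusion of case B from the TEAE tables, and attribution of case C to the Month 1 product only, both depend on a worsened event staying as one record with its original start. Case C further depends on events being attributed by that start.

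The exposure is mainly for AEs outside the four scored symptoms. No overall size or direction of bias can be given; a percentage loss would only hand back whatever rates were assumed. The figure of 5.0 points per patient at 20 patients shows sensitivity and does not estimate harm. The change is worth making because the tables are small and the rule is easily completed.

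**What to change.** In SAP 13.2:

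- Define a TEAE as an AE that starts, or increases in severity, at or after first dose.
- Apply the same test again at the first dose of Month 2.
- Assign each onset or worsening to the product most recently started, including during the break between cycles.
- Date a worsening at the change in severity, through a new AE record with its own start and severity.

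SAP section 16 describes the ages of the enrolled patients in the past tense, so enrolment may already have been known when it was written. If data collection has ended, a new instruction to sites would come too late, and the dates of worsening would have to be obtained by data query.

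The cost is SAP wording, a few more AE records or queries, and slightly higher reported incidence.
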